11.7.1.3 Sensitivity Analyses

To evaluate the impact of important protocol deviations and missing data, sensitivity analyses will be performed using the analysis methods described for the FDA equivalence and EMA non-inferiority analyses:

- 1) PPS: Using MI approach as described for main HbA1c analysis. If in the number of subjects who discontinued treatment and return to provide an HbA1c sample at Week 26 is insufficient to perform the MI, the MI will instead be performed using data from all patients with HbA1c results at Week 26 in each treatment group under the assumption of MNAR. (Table 5, Analysis 2)
- 2) FAS Completers: This analysis will not use any imputation of missing data. Only subjects with valid baseline and visit Week 26 assessment conducted at actual visit Week 26 visit and who had treatment until visit Week 26 will be used for the analysis. (Table 5, Analysis 3)
- 3) Per Protocol Analysis Set 3 (PPS3) - Subjects with any efficacy-interfering important protocol deviations (EIIPD; as defined in Section 11.3) will be excluded from the analysis. For the subjects in the PPS3, the imputation approach as described for the main analysis will be followed. In the main analysis, subjects with efficacy-interfering important protocol deviations could falsely draw the estimated treatment difference closer. Exclusion of these subjects in this sensitivity analysis will help assess the magnitude, if any, of this effect. (Table 5, Analysis 4)
- 4) Mixed model repeated measure (MMRM): this sensitivity analysis will include all post-baseline HbA1c measures from each time point as the dependent variable. The independent variables in the model include fixed effects for treatment assignment (2 levels), time (3 post-baseline times), treatment-by-time interaction, country, and covariate terms for the baseline HbA1c score and baseline HbA1c score-by-time interaction (which allows the effect of baseline covariate parameter to change over time). An unstructured covariance matrix will be used to model the inter-dependencies among the repeated measures. However, if the model does not converge, an alternative covariance matrix will be used which is appropriate for the repeated measurements (e.g., first-order autoregressive). Given the missing data, the Kenward-Roger approximation will be used for calculating the denominator degrees of freedom and adjusting standard errors. If a structured variance-covariance matrix is used, sandwich estimator will be used to estimate the variance of the treatment effect estimate. The FAS will be used to generate the results. (Table 5, Analysis 5)

instead examine the results under a MNAR assumption. If the tipping point analysis reveals that the "tipping point" is at an unreasonable shift, then the robustness of the study results under the MAR assumption are supported.

A sample SAS code fragment is provided below for reference (note: actual seeds to be used in the analysis are presented below):

```
proc mi data=<data> nimpute=10 seed= 337850 out=<out_data> minimum=. 0 0;  
  class trt;  
  monotone reg;  
  mnar adjust(week_26 /shift = <shift> adjustobs=(trt='Gan & Lee Insulin Glargine Injection'))  
    adjust(week_26 /shift = -<shift> adjustobs=(trt='Lantus'))  
  var trt base_HbA1c week_26;  
run;
```

The following shift values will be used (increase for Gan & Lee Insulin Glargine Injection and decrease for Lantus® simultaneously): 0, 0.2, 0.4, etc. until the conclusion of equivalence or non-inferiority will change, the equivalence 2-way tipping point analysis utilizes a shift in both directions (additionally decrease for Gan & Lee Insulin Glargine Injection and increase for Lantus®). The ANCOVA analyses will be performed as described in Section 11.7.1.1.

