11.7 Efficacy Analyses

11.7.1 Key Secondary Endpoint

An overview of planned analyses for the key secondary endpoint of change from baseline in HbA1c, including sensitivity analyses, is provided in Table 5 below.

Table 5: Overview of key secondary endpoint analyses

Analysis	Population used	Analysis Details	Section reference
1. Main analysis	Full analysis set	Treatment Policy Estimand - ANCOVA using MI under the assumption of MNAR; this analysis uses unscheduled HbA1c results from discontinued subjects to impute missing in each treatment arm.	Section 11.7.1.1 Change from Baseline in HbA1c at 26 weeks
2. Sensitivity analysis	Per protocol analysis set	ANCOVA using MI under the assumption of MNAR; this analysis uses the same approach for imputation as the main analysis. Used to assess the robustness of main analysis to important deviations from the protocol.	Section 11.7.1.3 Sensitivity Analyses - PPS
3. Sensitivity analysis	Full analysis set of completers	ANCOVA without imputation. This analysis is used to assess the robustness of main analysis to subjects lost to follow-up.	Section 11.7.1.3 Sensitivity Analyses - FAS completers

For subjects who discontinue from treatment before visit Week 26 or who have no HbA1c measurement at visit Week 26, HbA1c will be assigned to the scheduled time point if they fall within the upper limit of visit window defined in Section 7.1 (that is, for study day ≤ 210).

Submissions to Food and Drug Administration (FDA) and European Medicines Agency (EMA) require different methods for efficacy HbA1c evaluation.

For FDA submission, equivalence in change from baseline in HbA1c between Gan & Lee Insulin Glargine Injection (μ_1) and Lantus® (μ_2) will be tested using the two one-sided tests (TOST) approach proposed in Schuirmann (1987) (7) with the following null hypothesis:

$$H_0: (\mu_1 - \mu_2) \leq -0.4 \text{ or } (\mu_1 - \mu_2) \geq 0.4$$

Against the alternative hypothesis of:

$$H_1: -0.4 < (\mu_1 - \mu_2) < 0.4$$

with $\alpha=0.05$.

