The 90% CI will be estimated using a pattern mixture model that uses multiple imputation (MI) analyzed using Analysis of Covariance (ANCOVA) with treatment and stratification factor of country (CNTRY) included as fixed effects and baseline HbA1c included as a covariate. Separately in each treatment group, the imputation will use outcomes in subjects who discontinued treatment prior to Week 26 but returned to provide a visit Week 26 HbA1c sample to impute outcomes in subjects without actual visit Week 26 recorded results under the MNAR assumption. Limits of the imputed value will use the minimum of HbA1c values and the maximum of all HbA1c values assessed, and rounded to the nearest integer. These values are found in the database to be minimum as 5 and the maximum as 13. No imputation will be performed for missing baseline HbA1c. Equivalence will be assessed based on the 90% CI; no p-values will be computed. Change from baseline in HbA1c between Gan & Lee Insulin Glargine Injection and Lantus® will be considered equivalent if the 90% CI is within the margins (-0.4%, 0.4%).

For EMA submission, non-inferiority in change from baseline in HbA1c between Gan & Lee Insulin Glargine Injection and Lantus® will be tested using the following null hypothesis:

$$H_0: (\mu_1 - \mu_2) \geq 0.4$$

Against the alternative hypothesis of:

$$H_1: (\mu_1 - \mu_2) < 0.4$$

with a 1-sided $\alpha=0.025$.

In addition, the same non-inferiority test with a margin of 0.3% will be performed.

The 95% CI will be estimated using a pattern mixture model that uses MI analyzed using ANCOVA with treatment and stratification factor of country (CNTRY) included as fixed effects and baseline HbA1c included as a covariate. Separately in each treatment group, the imputation will use outcomes in subjects who discontinued treatment prior to Week 26 but returned to provide a visit Week 26 HbA1c sample (labeled as the unscheduled) to impute outcomes in subjects without actual visit Week 26 recorded results under the MNAR assumption. No imputation will be performed for missing baseline HbA1c.

Analysis of HbA1c will follow a hierarchical testing strategy: first, non-inferiority will be tested using a margin of 0.4% and only if this test is significant, then non-inferiority will be tested using a margin of 0.3%.

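### The FAS completers HbA1c analysis cannot isolate the effect of loss to follow-up, because its rule also drops subjects who stopped treatment but were measured at Week 26

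*SAP*

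**What the plan says.** SAP Section 11.7.1, Table 5, describes Analysis 3 (population: FAS completers) as follows: "ANCOVA without imputation. This analysis is used to assess the robustness of main analysis to subjects lost to follow-up".

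SAP Section 11.7.1.3, item 2, gives the rule. There is no imputation ("FAS Completers: This analysis will not use any imputation of missing data"), and the subjects kept are "Only subjects with valid baseline and visit Week 26 assessment conducted at actual visit Week 26 visit and who had treatment until visit Week 26".

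The main analysis treats subjects who stopped IP and came back quite differently. For subjects who stop treatment early or lack a Week 26 measurement, "HbA1c will be assigned to the scheduled time point if they fall within the upper limit of visit window", that is, up to study day 210. These values also feed the imputation in each arm: "the imputation will use outcomes in subjects who discontinued treatment prior to Week 26 but returned to provide a visit Week 26 HbA1c sample".

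Protocol Section 12.8.1 sets a treatment policy estimand for HbA1c. It counts subjects who discontinued treatment but gave a Week 26 sample among those who completed the study. SAP Section 5.1 reports that early discontinuation was higher than expected and that Amendment 3 added procedures to bring such subjects back.

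**The concern.** Table 5 gives Analysis 3 one purpose, robustness to loss to follow-up. A subject who stopped IP, returned and was measured has been followed. The inclusion rule still removes that subject, because it requires treatment until Week 26 as well as a Week 26 value. Three things therefore change at once relative to the main analysis:

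- imputed values are removed;
- observed off-treatment values are removed;
- the sampling window may narrow from day 210 to the actual visit.

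Only the first concerns loss to follow-up. If the two analyses disagree, the reader cannot say which change caused it. If they agree, the reader cannot say that loss to follow-up was harmless. What is at stake is the interpretation of one supportive analysis of the key secondary endpoint.

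**Working it through.** The documents give no HbA1c sample size, SD, stopping rate or return rate, so there is no figure of the plan's own to reproduce. The check compares the rules and then uses expected-value algebra with assumed rates.

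**Step 1. Who contributes what** (SAP Sections 11.7.1 and 11.7.1.3)

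| Subject | Main analysis | FAS completers |
|---|---|---|
| On treatment, sampled at the Week 26 visit | own value | own value |
| On treatment, sampled outside that visit but by day 210 | own value | possibly excluded |
| Stopped IP, returned with a sample by day 210 | own value, and imputation donor | excluded |
| No Week 26 value | imputed from returners in the same arm | excluded |

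Only the last row is loss to follow-up.

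**Step 2. Expected values.** In each arm let d be the share who stop IP, r the fraction of stoppers who return, and g the mean Week 26 HbA1c of stoppers minus that of on-treatment completers. Simplifications: all lost subjects are stoppers, lost subjects take the returners' mean (the SAP's imputation rule), and covariate adjustment is ignored. Relative to the completer mean:

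- main = d·g
- FAS completers = 0
- all observed Week 26 values, no imputation = d·r·g / (1 − d + d·r)

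For test arm T and reference arm R, the expected gap is

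completers − main = −(d_T·g_T − d_R·g_R).

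The return fraction r does not appear, so the gap is the same whether few or many stoppers are lost. The all-observed analysis equals main when r = 1 and departs from it only when someone is lost.

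**Step 3. Illustrations** (all rates and values of g assumed; entries are T − R in HbA1c percentage points, with no difference among completers)

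| d, T / R | g, T / R | Stoppers lost | Main | Completers | All observed |
|---|---|---|---|---|---|
| 20% / 10% | 0.5 / 0.5 | 0% | 0.050 | 0.000 | 0.050 |
| 20% / 10% | 0.5 / 0.5 | 50% | 0.050 | 0.000 | 0.029 |
| 15% / 10% | 0.5 / 0.5 | 0% | 0.025 | 0.000 | 0.025 |
| 15% / 10% | 0.5 / 0.5 | 50% | 0.025 | 0.000 | 0.014 |
| 15% / 10% | 0.5 / 0.5 | 90% | 0.025 | 0.000 | 0.003 |
| 10% / 10% | 0.5 / 0.5 | 0% or 50% | 0.000 | 0.000 | 0.000 |

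Second row in full: main = 0.20 × 0.5 − 0.10 × 0.5 = 0.050; all observed = 0.10 × 0.5 / 0.90 − 0.05 × 0.5 / 0.95 = 0.0556 − 0.0263 = 0.029. In the first row nobody is lost, yet the completers result still moves by 0.050. The largest shift among the settings tried was 0.10 (20% against 10% stopping, g = 1.0 in both arms).

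**Step 4. How much of the shift is deleted observed data.** Let d and r be equal in both arms, and let D be the between-arm difference among stoppers minus that among completers. The move from main to completers has size d·D. The part between all-observed and completers has size d·r·D / (1 − d + d·r). The ratio is

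share = r / (1 − d + d·r),

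which does not depend on D (provided D is not zero).

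| d | r = 1/3 | r = 1/2 |
|---|---|---|
| 10% | 0.333 / 0.933 = 36% | 0.500 / 0.950 = 53% |
| 15% | 0.333 / 0.900 = 37% | 0.500 / 0.925 = 54% |
| 20% | 0.333 / 0.867 = 38% | 0.500 / 0.900 = 56% |

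**The case against.** The best defence is that this is a labelling slip. The Table 5 row openly names a completer population. Section 11.7.1.3 opens with a wider aim covering both deviations and missing data. The parallel antibody analysis in SAP Section 11.6.1.3 also requires treatment until Week 26 and says that its purpose is full treatment duration. An on-treatment completer set therefore looks deliberate. This stands as a reason to keep the current analysis. It does not make that analysis a check on loss to follow-up, which is the purpose that Table 5 states.

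A reader might infer that the plan has no sound check on missing HbA1c data. The documents do not support that. The MMRM in Section 11.7.1.3 uses all post-baseline HbA1c values in the FAS without specifying imputation, and the tipping-point analysis shifts the Week 26 values. Only the first three rows of Table 5 and part of the surrounding text are available here, so another observed-data analysis may be listed. What remains is that Analysis 3 does not do its own stated job.

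A reader might also infer that the completer subset leans toward no difference, because Protocol Section 8.4.3.1 allows withdrawal for inadequate response. That is one reason among several, with no frequency given. Selection of good responders in both arms does not by itself bias the between-arm difference, and Step 3 shows no shift when stopping rates and effects match.

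**Conclusion.** The point holds for Analysis 3 as written: its inclusion rule does not match the purpose in Table 5. Under the SAP's own imputation rule, the expected gap between it and the main analysis is set by all treatment stoppers and carries no information on the number lost.

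Neither direction nor size follows from the documents. With equal stopping rates and effects the shift is zero. With 10-20% stopping and one third to one half returning, equal in both arms and with returners representing the lost, about 36-56% of any shift would come from deleting observed data. In the illustrations the total shift is at most 0.10 against the 0.4 margin, but that depends wholly on the assumed inputs.

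It would be wrong to conclude that the equivalence or non-inferiority result is at risk. Those decisions rest on the main FAS analysis, which this does not touch. The change is worth making at the level of a supportive analysis.

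**What to change.** For the loss-to-follow-up check, run the same ANCOVA without imputation in all FAS subjects who have a baseline and an observed Week 26 HbA1c in the main-analysis window (study day ≤ 210), on or off treatment. Enter this in Table 5 with the purpose now given to Analysis 3. Keep the current analysis as a separate row, relabelled as on-treatment completers, and state its purpose as such.

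The cost is brief SAP text and one extra supportive model run on data already in the FAS, reported with the 90% and 95% intervals used elsewhere. The new analysis is also model-based: it assumes that missingness is ignorable given treatment, country and baseline HbA1c, and it does not use the Week 8 and Week 16 values as the MMRM does. It adds to the MMRM and tipping-point analyses and does not replace them.

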## 12.8 Key Secondary Endpoint

### 12.8.1 Change from Baseline in HbA1c at 26 Weeks

The key secondary analysis will be to evaluate equivalence (FDA)/noninferiority(EMA) of Gan & Lee Insulin Glargine Injection relative to Lantus® for HbA1c by comparing the 90% confidence interval with (-0.4%, 0.4%) for equivalence using the TOST approach and by comparing the upper limit of the 95% CI with 0.4% for noninferiority from a pattern mixture model that uses multiple imputation analyzed using Analysis of Covariance (ANCOVA) with treatment and stratification factor of country included as fixed effects and baseline HbA1c included as a covariate. Separately in each treatment group, the imputation will use the outcomes of patients who completed the study (including subjects who discontinued treatment but provided a visit Week 26 HbA1c sample) to impute outcomes in patients without actual visit Week 26 recorded results under the missing at random assumption. Full details of the multiple imputation procedure will be specified in the SAP. Analysis of HbA1c will follow a hierarchical testing strategy: first, equivalence/noninferiority will be tested with a margin of 0.4%; secondly, if and only if the test using a margin of 0.4% is significant, then equivalence will be tested using a margin of 0.3%. Analyses of HbA1c in the testing hierarchy will be conducted on the Full Analysis Set consisting of all randomized subjects according to randomized treatment with supportive analyses on the Per Protocol Analysis Set. A tipping point analysis with varying assumptions about the differences on each treatment arm between outcomes in patients who withdrew from the study early and outcomes in patients who completed the study will be performed. The estimand of interest for the HbA1c analysis is the difference in change from baseline for HbA1c using the “treatment policy strategy”.

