5.1 Sample Size and Power

Enrollment was planned for 550 subjects overall (275 subjects per treatment group). The primary analysis for the immunogenicity primary endpoint was to be an equivalence test for the difference in proportion of subjects who develop treatment-induced AIAAs between Gan & Lee insulin Glargine Injection and Lantus® using the 2 Wald one-sided tests (TOST) with $\alpha=0.05$ (Chow and Shao 2002 (1)). After scientific and regulatory review, the method to evaluate immunogenicity equivalence will be the 90% confidence intervals of risk difference from the logistic regression analysis (see Section 3.1). Under this newly adopted approach, no power loss is expected.

This sample size of 275 subjects per treatment group was chosen to achieve over 80% power using the TOST equivalence test for two proportions, a risk difference of zero and equivalence margins dependent on the observed treatment-induced AIA rate per Table 3 below. For example, a total sample size of 550 will provide approximately 85% power for the TOST equivalence test using a treatment-induced AIA rate of 30% and a margin of 12% (Table 3). The treatment-induced AIA is defined as newly confirmed positive AIA development or important (at least a 4-fold) increase in AIA titers, after baseline and up to visit Week 26 (see the definition of Primary Endpoint in Section 6.1 and Section 7.2). No drop outs are considered in the calculation. A larger than expected early discontinuation rate was observed as part of study monitoring activities and therefore protocol amendment 3 approved on 25-Apr-2019 included procedures to encourage subjects to return for assessments even if they had discontinued treatment early.

The appropriate similarity margin, based on the actual observed event rate for the intended reference product, will be used for final analysis after database lock as summarized in Table 3 below. The power calculation in the table was adapted for a sample size of 550 using the treatment-induced AIA rate for the reference product. Linear interpolation will be used for values between AIA rates in the table.

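### The HbA1c tipping-point analysis starts from a different imputation than the main analysis, so shift 0 does not reproduce the main result and the tipping shift tends to be overstated

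*SAP*

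**What the plan says.** **Main analysis (SAP 11.7.1 and Table 5).** In each arm separately, the outcomes of subjects who stopped treatment early but came back for a Week 26 sample are used "to impute outcomes in subjects without actual visit Week 26 recorded results under the MNAR assumption". Imputed values are limited to 5 to 13. The result is analysed by ANCOVA with treatment, country and baseline HbA1c.

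**Tipping point (SAP 11.7.1.3).** The sample code is a single PROC MI call ("nimpute=10 seed= 337850") in which treatment and baseline HbA1c are the only predictors of Week 26 HbA1c. It does not process the arms separately, has no restriction to returning subjects and no term for discontinuation. The lower bound is 0 and there is no upper bound. Imputed values are raised in the test arm and lowered in the Lantus arm in steps of 0.2 until the conclusion changes; for equivalence the reverse direction is run too. If the tipping shift is unreasonable, "then the robustness of the study results under the MAR assumption are supported".

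**Protocol 12.8.1.** The protocol's main imputation was MAR, by arm, from everyone with a Week 26 value. It asks for "A tipping point analysis with varying assumptions about the differences on each treatment arm between outcomes in patients who withdrew" early and those who completed. Protocol 12.6.1 says that the robustness of the HbA1c imputation will be explored by sensitivity analyses that include a tipping point.

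**The concern.** A tipping-point analysis says how far the imputed values must move before a claim fails. It answers that only if the unshifted run is the analysis that carries the claim. Here the SAP has replaced the protocol's MAR imputation by one from returning subjects, while the tipping point still starts from MAR and draws its conclusion about MAR. The per-protocol sensitivity analyses (PPS and PPS3) in the same section do carry over the main imputation.

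The two starting points also differ in precision. An imputation that borrows from every observed subject carries little uncertainty; one that rests on a handful of returning subjects per arm carries much more. A narrower starting interval leaves more room before the ±0.4 limit, so the tipping shift would tend to look more reassuring than the main analysis warrants. The SAP expects that returning subjects may be too few for the imputation (said for the PPS) and reports that "A larger than expected early discontinuation rate was observed as part of study monitoring activities". What is at stake is how the equivalence and non-inferiority claims on the key secondary endpoint are defended against missing data.

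**Working it through.** **1. Design inputs.** SAP 5.1: "Enrollment was planned for 550 subjects overall (275 subjects per treatment group"). Its one worked power example, "using a treatment-induced AIA rate of 30% and a margin of 12"%, gives SE = √(2 × 0.3 × 0.7 / 275) = 0.0391 and power = 2Φ(0.12/0.0391 − 1.645) − 1 = 84.6%, against about 85% stated. This confirms 275 per arm and α = 0.05 but says nothing about HbA1c. On missing data the section says "No drop outs are considered in the calculation". The documents provided give no HbA1c SD, missing rate or number of returning subjects, so these must be assumed.

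**2. Assumptions.** Baseline SD 1.0; residual SD 0.8 (1.1 as a check); 5, 10 or 15% missing per arm; 5, 10 or 20 returning subjects per arm; true difference 0. Ten imputations were used for both methods, with Rubin's rules and ANCOVA on treatment and baseline. Country was omitted.

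**3. Hand check of the code's starting interval.** With 15% missing, the MAR half-width is about 1.645 × 0.8 × √(2 / (275 × 0.85)) = 0.122. The simulation gave 0.123.

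**4. Tipping formula.** With a fraction d missing per arm, shifts of +s and −s move the difference by 2ds. From a zero difference with half-width h, equivalence is lost at s = (0.4 − h)/(2d). For 15% missing and 5 returning subjects per arm:
- code: (0.4 − 0.123)/0.30 = 0.92
- main-type: (0.4 − 0.228)/0.30 = 0.57

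**5. Simulation.** Median 90% CI half-width at shift 0 (300 trials) and mean first failing shift against +0.4 on the SAP's 0.2 grid (150 trials), residual SD 0.8:

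| Missing | Returning per arm | Half-width, code | Half-width, main-type | Ratio | Shift, code | Shift, main-type | Excess |
|---|---|---|---|---|---|---|---|
| 5% | 10 | 0.115 | 0.123 | 1.07 | 2.65 | 2.58 | 0.07 |
| 10% | 20 | 0.118 | 0.129 | 1.09 | 1.40 | 1.36 | 0.04 |
| 10% | 10 | 0.119 | 0.143 | 1.20 | 1.48 | 1.35 | 0.13 |
| 10% | 5 | 0.119 | 0.174 | 1.46 | 1.44 | 1.11 | 0.33 |
| 15% | 20 | 0.122 | 0.141 | 1.16 | 0.99 | 0.93 | 0.06 |
| 15% | 10 | 0.123 | 0.167 | 1.36 | 0.97 | 0.84 | 0.13 |
| 15% | 5 | 0.123 | 0.228 | 1.86 | 1.00 | 0.60 | 0.40 |

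Over all 13 scenarios run, the code's interval was the narrower one in 89 to 99% of trials. With residual SD 1.1, 15% missing and 10 returning subjects, the shifts were 0.86 and 0.70. The 95% CI against 0.4 behaved alike: 0.89 and 0.47 with 15% missing and 5 returning, 2.39 and 2.33 with 5% missing and 10 returning. The 0.3 margin was not run.

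**6. How reliable the direction is.** With no arm difference among discontinuers (90% CI), the code's shift was larger in 33 to 74% of trials, equal in 11 to 54% and smaller in 8 to 25%. With 15% missing and 10 returning subjects:
- test-arm discontinuers 0.3 worse: 0.99 against 0.67, larger in 82% of trials
- test-arm discontinuers 0.3 better: 1.05 against 1.04, larger in 39% and smaller in 35%

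**The case against.** **The MAR start follows the protocol.** Protocol 12.8.1 defines the tipping point by how early withdrawals differ from completers, and a shift away from a fit to all observed data is close to that. A shift from returning subjects is a different quantity, resting on few people. This stands as a reason to keep the MAR version. It does not make that version a test of the SAP's main analysis.

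**The size is uncertain and often small.** With 10 or 20 returning subjects per arm and SD 0.8, the mean excess is below the SAP's 0.2 grid step. This stands in full.

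**The text is incomplete.** The opening of the tipping-point paragraph and the main-analysis code are not in the text available, and the fragment is labelled a sample. An explicit link to some other MAR analysis cannot be ruled out. But the surviving prose and the code agree with each other, and the fragment carries the seed to be used.

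**The model is not fully pooled.** The treatment term keeps the arm means separate; only the slope and residual variance are shared. This is correct, but the source of the imputed values still differs. The separate effect of the bounds was not quantified.

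A reader might also infer two further faults that the documents do not support:

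- *Ten imputations narrow the interval.* They do not: Rubin's rules add B/m, so fewer imputations widen it. The number used in the main analysis cannot be seen, so no contrast can be drawn. For this code, with 6 to 16% of information missing, the Monte Carlo SD is about √(0.06/10) × 0.070 = 0.005 to √(0.16/10) × 0.0748 = 0.009, which is trivial beside 0.4.
- *Moving the arms only in opposite directions is an error.* The protocol asks for varying assumptions on each arm, not independent ones. Opposite shifts are the harsher path: moving one arm alone would tip at (0.4 − 0.123)/0.15 = 1.85 rather than 0.92. An independent grid is a preference.

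**Conclusion.** The mismatch is established from the text alone. The main analysis imputes by arm from returning subjects, labelled MNAR and limited to 5 to 13. The tipping point starts from one MAR model on all observed values and concludes about MAR. Its unshifted run will not in general equal the main result, so it cannot show how far that result is from failing, whichever way the numbers fall.

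The numerical effect is a tendency. The starting interval is expected to be narrower (half-width ratio 1.07 to 1.86). Under the stated assumptions the mean tipping shift is too large by 0.04 to 0.13 with 10 or 20 returning subjects per arm, and by about 0.3 to 0.4 with only 5 and 10 to 15% missing. A reader might infer that robustness is necessarily overstated. The documents do not support that: they give no SD, missing rate or number of returning subjects, and the excess is small with little missing data or about 20 returning subjects. On average it vanishes, and in single trials it can reverse, if test-arm discontinuers do better.

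This should be corrected. It affects one sensitivity analysis of the key secondary endpoint and leaves the main estimate unchanged.

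**What to change.** - Apply the shifts to the imputed values of the main analysis: the same by-arm model from returning subjects, the same bounds before shifting, the same number of imputations and the same ANCOVA. State that shift 0 must reproduce the main estimate and interval.
- Reword the conclusion as robustness of the main analysis under its own MNAR assumption.
- Keep the MAR-based version as an additional sensitivity analysis, labelled as the protocol's completer-based comparison.
- Report the number of returning subjects and of missing Week 26 values by arm beside the tipping shift, so the reader can judge how firm the starting point is.
- Optional: shift each arm separately on a two-way grid, and use more imputations. The latter matters more once the imputation rests on few subjects: with 8 returning subjects per arm, a simulation of the main-type estimate gave a Monte Carlo SD of 0.023 at 10 imputations and 0.008 at 100.

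The cost is SAP wording, code and minutes of computing; no new data are needed. The reported tipping shift may be less favourable, and with few returning subjects the starting point is itself imprecise.
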